8.1.1 Screening/Visit 1 (-14 days to Day 0)

The screening and baseline visits may be performed on the same day; however, a maximum of 14 days is allowed between the screening and baseline visits.

 GALDERMA	Title 43QMI902 Clinical Study Protocol - QM1114 - LCL and GL	Doc id MA-40371
--	---	----------------------------------

At the screening visit, the Investigator or designee will:

1. Review and explain the nature of the study to the subject, particularly the prohibited activities and constraints (e.g., restrictions for other aesthetic treatments and the use of topical and systemic medications, see Section [5.4.5](#)).
2. Obtain the signed and dated ICF (inclusive of HIPAA and photo consent); provide a fully completed dated and signed copy to the subject.
3. Collect information regarding demographics (i.e., date of birth, gender, race, ethnicity, height, and weight), Fitzpatrick skin type, relevant medical history and concurrent diseases, previous facial treatments/procedures (including toxin naïve/non-toxin naïve), previous medications and procedures, and concomitant medications and procedures (see [Table 2 Schedule of Assessments](#)).
4. Instruct the subject on how to complete the LCL-SLA at **CCI** maximum smile. Subject to complete self-assessments using the 4-point Photographic Scales (LCL-SLA). LCL severity of Level 2 or Level 3 on the LCL-SLA at maximum smile, as assessed by the subject, is required for study inclusion. (Section [7.1.2](#) and [Appendix 2](#))
5. Instruct the subject on how to complete the GL-SLA at maximum frown. Subject to complete self-assessment using the Static 4-point Categorical Scales (GL-SLA). Moderate to severe GL (score of 2 or 3 on the Static 4-point Categorical Scale) at maximum frown, as assessed by the subject, is required for study inclusion. (Section [7.1.4](#))
6. Investigator to complete assessment of the subject's bilateral LCL severity at **CCI** maximum smile using the 4-point Photographic Scales (LCL-ILA). Moderate to severe bilaterally symmetrical LCL (grade 2 or 3 on the LCL-ILA) at maximum smile, as assessed by the Investigator, is required for study inclusion. (Section [7.1.1](#) and [Appendix 1](#))

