Version: 1.0

Concomitant medications for this study are defined as any ongoing medications with a start date prior to the date of injection, any changes to existing medications (such as dose or formulation) during the course of the study, or any new medications received by the subject since the date of injection. Prior medications are medications with stop dates prior to study treatment and used within 4 weeks preceding screening visit. Medications will be coded using the World Health Organization (WHO) Drug Dictionary, concomitant procedures will be coded according to MedDRA. The versions used for the coding will be noted as a footnote in the tables and listings.

The number and percentage of subjects who receive prior and concomitant medications will be summarized by the WHO Drug Dictionary Anatomical Therapeutic Chemical 3rd level (ATC-3) and the preferred name. If the 3rd level term is not available, the next available level (e.g., ATC-2) will be used. In addition, the number and percentage of subjects reporting a concomitant medication/therapy will be summarized by reason (medical history, adverse event, concomitant procedure, contraception, or other). Therapies and procedures that started due to an AE will be summarized separately from those who did not start due to an AE.

ATC-3 and preferred name will be presented in descending frequency first based on the QM1114-DP in GL/QM1114-DP in LCL group, and then alphabetically if there are ties. Each subject will contribute at most one count per summarization category. In other words, if a subject has more than one medication with same preferred name, the subject will be counted only once for that preferred name. Similarly, if a subject has more than one medication for an ATC-3 level, the subject will be counted only once in that ATC-3 level and preferred name. Concomitant procedures will also be presented and will follow the same methods specified for medical history.

Prior and concomitant medications/procedures will be presented by subject in a data listing.

Handling of Missing/Partial Dates

While every effort will be made to obtain full, complete information on every reported medication, the following imputation rules will be followed for any respective missing medication data:

For the purpose of determining whether a medication is considered prior or concomitant, the following date imputation rules will be used. Dates will be presented as collected in the listings.

- Start Date

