 - If the start date is completely missing, it will be assumed that the medication started on the study treatment date.
 - If the start date is missing the day, the first of the month will be used (i.e. UNK-JAN-2019 becomes 01-JAN-2019), provided the imputed date is on or after the subject's study treatment date; otherwise, the day of study treatment will be used.
 - If the start date is missing the month, the month of 'June' will be used (i.e. 01-UNK-2019 becomes 01-JUN-2019), provided the imputed date is on or after the subject's study treatment date; otherwise, the subsequent month after study treatment will be used.
 - If the start date is missing the year, the year of study treatment will be used (i.e. 01-JAN-UNK becomes 01-JAN-2019), provided the imputed date is on or after the subject's study treatment date; otherwise, the subsequent year after treatment will be used.
- End Date

 GALDERMA	Title 43QMI902 Statistical Analysis Plan US - QM1114-DP - GL&LCL	Doc id MA-43265
--	---	----------------------------------

2021-02-05 13:16

Effective date:

Effective

Version: 1.0

- If the end date is completely missing, it will be assumed that the medication is still ongoing and will not be imputed.
- If the end date is missing the day, the last day of the month will be used (i.e. UNK-JAN-2019 becomes 31-JAN-2019).
- If the end date is missing the month, the subsequent month after the start date will be used.
- If the end date is missing the year, the year of study treatment will be used (i.e. 01-JAN-UNK becomes 01-JAN-2019), provided the imputed date is after the start date; otherwise, the subsequent year after start date will be used.

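### The SAP's rule for a medication stop date with unknown month ignores the injection date, so a drug that may still have been in use at injection can be classed as stopped before it

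*SAP*

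**What the plan says.** SAP 2.3.4, under Handling of Missing/Partial Dates, states the purpose of the rules: "For the purpose of determining whether a medication is considered prior or concomitant, the following date imputation rules will be used".

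The two definitions that the imputed date must serve stand earlier in the same section:

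- Concomitant, for a drug begun before injection: "any ongoing medications with a start date prior to the date of injection". Changes to existing drugs and new drugs since injection also count.
- Prior: "Prior medications are medications with stop dates prior to study treatment and used within 4 weeks preceding screening visit".

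The end-date bullets are:

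- Wholly missing: "If the end date is completely missing, it will be assumed that the medication is still ongoing and will not be imputed".
- Day missing: the last day of the recorded month.
- Month missing: "If the end date is missing the month, the subsequent month after the start date will be used".
- Year missing: the year of study treatment, "provided the imputed date is after the start date; otherwise, the subsequent year after start date will be used".

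The same missing-month sentence appears in the adverse-event date rules in SAP 2.5.2. SAP 2.8, which lists departures from the protocol's analyses, does not mention either rule.

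**The concern.** For a drug begun before injection, the prior/concomitant split depends on whether it was still being taken at injection. Three of the four end-date bullets respect what is known: a wholly missing stop is left open, a missing day goes to the latest day possible, and a missing year is checked against the start. The missing-month bullet places the stop just after the start and checks nothing.

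A stop known to lie in the year of injection can therefore be put before injection, while a stop about which nothing is known counts as ongoing. More information can give a worse classification. If the imputed stop also precedes the four-week window before screening, the drug fits neither definition and can drop out of both Table 14.1.7.1 (prior) and Table 14.1.7.2 (concomitant).

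**Working it through.** **Inputs.** The bullets and definitions above come from SAP 2.3.4. Protocol 8.1.1 says that "a maximum of 14 days is allowed between the screening and baseline visits". The documents give no individual injection dates, so those below are assumptions. There is no plan figure to reproduce beyond the worked example for a missing day (UNK-JAN-2019 becomes 31-JAN-2019), which the coded rules return.

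**Two readings of the rule.** The recorded day is kept and the month becomes start month + 1 (December goes to January).
- Keep-year: the recorded end year is kept.
- Roll-over: the year is that of the calendar month following the start.

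**Example 1: a drug possibly in use at injection.** Injection is assumed on 06-JUL-2020; start 10-FEB-2020, stop 20-UNK-2020.
- Imputed stop, both readings: 20-MAR-2020, before injection, so not ongoing.
- Stops that fit the record: the 20th of February to December, 11 dates. Six of them (July to December) are on or after injection.
- Four-week window: screening is at the earliest 06-JUL minus 14 days = 22-JUN-2020. Minus a further 28 days, the window opens on 25-MAY-2020. Since 20-MAR is earlier, the drug is not prior either.
- With the stop wholly missing, the same drug would be concomitant.

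**Example 2: December start, same recorded year.** Start 15-DEC-2019, stop 20-UNK-2019.
- Keep-year: 20-JAN-2019, before the start.
- Roll-over: 20-JAN-2020, against the recorded year.
- The only date the record allows is 20-DEC-2019.
- Taking every start day and every end day on or after it gives 31 × 32 / 2 = 496 combinations. All 496 fail, in one way or the other according to the reading. A December start with a stop recorded in the following year causes no reversal.

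**Calendar grid.** This covers all starts from 01-JAN-2020 to the day before injection, all end days, and end year 2020. Of the combinations that give a valid date and allow a stop on or after injection, the share imputed as stopped before it is:

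| Assumed injection | Share classed as stopped |
|---|---|
| 15-MAR-2020 | 1305/2218 = 59% |
| 15-JUN-2020 | 4092/5022 = 81% |
| 15-SEP-2020 | 6913/7843 = 88% |

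With screening 14 days before injection, 2818 of the 4092 and 5611 of the 6913 also miss the four-week window. These are shares of date combinations, not of subjects. A few further combinations give impossible dates, such as 31 February.

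**Simulation.** Assumptions: injection 06-JUL-2020, exit 21-DEC-2020, start uniform over the look-back before injection, stop uniform from start to exit, month missing.

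| Look-back (days) | 180 | 365 | 730 |
|---|---|---|---|
| In use at injection, classed as stopped: keep-year | 77% | 58% | 57% |
| In use at injection, classed as stopped: roll-over | 77% | 86% | 90% |
| Stopped before injection, classed as in use: keep-year | 4% | 36% | 24% |
| Total misclassified: keep-year | 54% | 48% | 37% |
| Total misclassified: latest-consistent-date rule | 32% | 37% | 32% |

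A rerun agreed to within about 1 percentage point.

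**The case against.** The strongest reply is that the rule will seldom be used. Protocol 5.4.3 and Table 2 have concomitant therapies reviewed at every visit (Days 7 and 14, then monthly), so a drug taken at baseline and stopped during follow-up should normally have its stop placed within about four weeks. The uniform dates in the simulation are assumptions. This stands, and it limits how many records are affected. It does not make the rule sound for those records.

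Four stronger readings are tempting, and the documents do not support them.

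- *Concomitant use is undercounted for every partial stop date.* Missing-day and missing-year stops have their own rules. Partial or missing starts are moved to or after treatment, which makes those drugs concomitant. Only missing-month stops with a fully known pre-injection start are exposed.
- *The error always hides exposure.* Under the keep-year reading it also runs the other way, for 4% to 36% of drugs truly stopped. A net undercount across the tables is not shown.
- *The December reversal corrupts the classification.* It need not. With injection on 06-JUL-2020, all three dates in Example 2 fall before injection.
- *Prohibited drugs could escape notice, or the per-protocol set could change.* Protocol 5.4.5 sends prohibited therapies to the Medical Monitor, and SAP 2.3.2 bases exclusions on team review of deviations before unblinding. Nothing routes either through this imputation, and listings show dates as collected.

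**Conclusion.** The point holds as a minor defect. As written, the missing-month bullet can class a drug possibly in use at injection as already stopped, can leave it outside both definitions, and for a December start with the same recorded end year returns a date that contradicts the record. It is out of line with the bullets around it.

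The damage shown is to descriptive medication tables. No efficacy or per-protocol analysis is shown to depend on the rule, and the number of affected records is unknown and probably small. The percentages describe how often the rule errs for a record to which it applies, under assumed dates. They say nothing about how many records there are.

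**What to change.** Replace only the missing-month end-date bullet in SAP 2.3.4 with:

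*If the end date is missing the month, the latest date consistent with the recorded day and year will be used, not before the start date and not after study exit.*

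The definitions of prior and concomitant, including the four-week condition for prior, and the other bullets stay as they are. Example 1 then gives 20-DEC-2020 (concomitant, with exit on 21-DEC-2020), and Example 2 gives 20-DEC-2019. Impossible dates no longer arise.

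The cost is one sentence and a small programming change, plus a change in the direction of error. In the simulation no drug truly in use at injection is lost, but 100%, 80% and 53% of those truly stopped (180-, 365- and 730-day look-back) are shown as concomitant. Total misclassification still falls, as tabulated, and this lean matches the SAP's own treatment of wholly missing stop dates.

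Review the identical adverse-event bullet in SAP 2.5.2 at the same time. There the imputed stop feeds event duration, so the replacement should be chosen for that purpose and not simply copied.

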2.4 Efficacy analysis

2.4.1 Datasets analyzed

The primary efficacy analysis will be analyzed based on the mITT population. All secondary efficacy **CCI** variables will be analyzed based on the ITT population, unless otherwise specified below. For GL analyses, the following treatment groups will be summarized separately: QM1114-DP in GL/placebo in LCL, QM1114-DP in GL/QM1114-DP in LCL, placebo in LCL/placebo in GL. Similarly for LCL analyses, the following treatment groups will be summarized separately: QM1114-DP in LCL/placebo in GL, QM1114-DP in LCL/QM1114-DP in GL, placebo in LCL/placebo in GL.

2.4.2 Handling of missing data

In general, the number of subjects with missing values will be summarized and reported as appropriate in all outputs. The primary analysis will be performed using multiple imputation (MI) as the primary imputation method and repeated using baseline observation carried forward (BOCF) as a sensitivity analysis for missing values. With the BOCF imputation method, if a subject is missing their Month 1 GL-ILA/GL-SLA scores or LCL-ILA/LCL-SLA Month 1 scores, their score at baseline will be used, respectively.

The imputation using MI will assume the Missing Completely at Random (MCAR) missing data assumption. Regardless of the actual pattern of missing data, the Markov Chain Monte Carlo (MCMC) method of the MI procedure from the SAS® system will first be used to create a monotonic pattern of missing data. Then, a second MI procedure will be used to generate five sets of data with missing values imputed from observed data. Linear regressions will be employed to model the missing GL-ILA, GL-SLA, left LCL-ILA, right LCL-ILA, left LCL-SLA, and right LCL-SLA scores separately, with the following covariates included in each imputation model: treatment group and non-missing ILA or SLA data, respectively for GL and LCL, from earlier timepoints (baseline, Day 7, and Day 14). The imputed datasets will be used to create the composite responder variable, which will then be analyzed using the methodology described for the primary analysis of responder rates at Month 1 ([Section 2.4.3](#)). The results from the analysis of the multiple imputed datasets will be combined by the MIANALYZE procedure of the SAS® system. The seed number to be used will be the number 110197.

The secondary efficacy analysis (described in [Section 2.4.4](#)) will be performed using the Observed Cases (OC), that is, no imputation will be done. **CCI**

	Title 43QMI902 Statistical Analysis Plan US - QM1114-DP - GL&LCL	Doc id MA-43265
--	---	----------------------------------

CCI

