9.2 Sample Size Determination

The sample size is determined by the number of subjects exposed to QM1114-DP in the LCL and GL, and amount of long-term safety data.

Further, due to the public health emergency related to the COVID-19 pandemic during 2020, steps have been taken to ensure patient and practitioner safety in alignment with FDA Guidance dated May 11, 2020 (*Guidance on Conduct of Clinical Trials of Medical Products during COVID-19 Public Health Emergency*). Most notably, in partnership with clinical sites and the IRB, optional remote assessment procedures for efficacy and safety endpoints has been implemented to ensure safety and respect localized and elective restrictions. Therefore, the sample size has been increased during the conduct of the study to ensure a sufficient number of subjects in the mITT population used in the assessment of the primary efficacy endpoint.

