1.1.2 Number of subjects and randomization

The study will screen approximately 454 male and female adults, 18 years of age and older, with moderate to severe glabellar lines at maximum frown and moderate to severe lateral canthal lines at maximum smile in up to 15 study sites in order to enroll 413 subjects. Following the screening process, eligible subjects will be randomized at the baseline visit (Day 0) in a 2:2:2:1 ratio to:

- 60 units QM1114-DP (60 units in the LCL and placebo in the GL, 118 subjects),
- 50 units QM1114-DP (50 units in the GL and placebo in the LCL, 118 subjects),
- 110 units QM1114-DP (60 units in the LCL and 50 units in the GL, 118 subjects), or
- Placebo in both the LCL and GL (59 subjects).

Randomization will be stratified by study center.

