Before unblinding the subject data, and as a part of preparations for the database lock, the study team will review all protocol deviations. All protocol deviations will be presented in a data listing.

Handling of Protocol Deviations During COVID-19

Due to the public health emergency related to the COVID-19 pandemic during 2020, steps have been taken to ensure patient and practitioner safety in alignment with FDA Guidance dated May 11, 2020 (Guidance on Conduct of Clinical Trials of Medical Products during COVID-19 Public Health Emergency). Most notably, in partnership with clinical sites and the Institutional Review Board (IRB), optional remote assessment procedures for efficacy and safety endpoints have been implemented to ensure safety and respect localized and elective restrictions.

Protocol deviations will be presented descriptively, overall and by treatment group. The total number of deviations, the type of protocol deviation, and if the deviation was reportable to the IRB

	Title 43QMI902 Statistical Analysis Plan US - QM1114-DP - GL&LCL	Doc id MA-43265
--	---	----------------------------------

will be summarized. These summaries will be stratified by relatedness to COVID-19 (related, not related). The above summary of protocol deviations will be repeated by site as well.

A listing of all protocol deviations reported throughout the study, including their relatedness to COVID-19, will be provided.

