2.4.3 Primary analysis

The primary efficacy endpoints will be the composite responder rate based on the GL-ILA and GL-SLA of GL severity at maximum frown at Month 1 (described in [Section 1.3.3](#) and [Section 1.3.4](#), respectively) as well as the composite responder rate based on the LCL-ILA and LCL-SLA of LCL severity at maximum smile at Month 1 (described in [Section 1.3.1](#) and [Section 1.3.2](#), respectively). To evaluate the effectiveness of QM1114-DP versus placebo in the treatment of moderate to severe LCL and GL, alone or in combination, the responder rates of the QM1114-DP and placebo will be compared using the Cochran-Mantel-Haenszel (CMH) test stratified by site at the 5% significance level (2-sided). The group treated in one rhytid area alone (the QM1114-DP in LCL/placebo in GL; the placebo in LCL/QM1114-DP in GL treatment groups) and the group with concurrent LCL and GL treatment (the QM1114-DP in LCL/QM1114-DP in GL treatment group) will be analyzed separately.

The null hypothesis of no relationship between treatment and responder rate will be tested against the alternative hypothesis that there is a relationship between treatment and responder rate. For a significant result, the two-sided p-value of the comparison of the composite GL-ILA/GL-SLA and composite LCL-ILA/LCL-SLA responder rates between the QM1114-DP treated and placebo treated subjects at Month 1 using the CMH test needs to be smaller than 0.05. The Breslow-Day test will be used to assess the homogeneity of the odds ratios across all sites.

To control the type I error rate among the 4 primary efficacy comparisons, the fixed sequence procedure will be used which requires no adjustment to the level of significance. The comparisons will be done in the following order:

1. GL alone group vs placebo on the **GL scale** (i.e. the placebo in LCL/QM1114-DP in GL group vs. the placebo in LCL/placebo in GL group)
2. GL + LCL group vs placebo on the **GL scale** (i.e. the QM1114-DP in LCL/QM1114-DP in GL group vs. the placebo in LCL/placebo in GL group)
3. LCL alone group vs placebo on the **LCL scale** (i.e. the QM1114-DP in LCL/placebo in GL group vs. the placebo in LCL/placebo in GL group)
4. GL + LCL group vs placebo on the **LCL scale** (i.e. the QM1114-DP in LCL/QM1114-DP in GL group vs. the placebo in LCL/placebo in GL group)

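### The primary multiple imputation is labelled MCAR although it relies on MAR, and site, which stratifies randomisation and the CMH test, is not in the imputation model; the expected effect is small

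*SAP*

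**What the plan says.** SAP 2.4.2 makes multiple imputation the primary method for missing Month 1 scores and declares: "The imputation using MI will assume the Missing Completely at Random (MCAR) missing data assumption". An MCMC step first makes the missing pattern monotone. A second step is to "generate five sets of data with missing values imputed from observed data", using separate linear regressions for six scores: GL-ILA, GL-SLA, and left and right LCL-ILA and LCL-SLA. The covariates are "treatment group and non-missing ILA or SLA data, respectively for GL and LCL, from earlier timepoints", namely baseline, Day 7 and Day 14. Site is not listed.

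Site is used in several other places:

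- SAP 1.1.2: "Randomization will be stratified by study center".
- SAP 2.4.3: the primary CMH test is stratified by site, and a Breslow-Day test checks whether odds ratios agree across sites.
- SAP 2.4.3.2 and 4.1: site is a subgroup for the primary endpoints, with Tables 14.2.1.5 and 14.2.2.5 run on imputed mITT data.

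On why data are missing, the summary of changes in Protocol 12.1 ties the move from BOCF to multiple imputation to COVID-19 and to more drop-outs and missing Month 1 data. Protocol 9.2 says that "optional remote assessment procedures for efficacy and safety endpoints has been implemented to ensure safety and respect localized and elective restrictions". SAP 2.2 removes subjects with a remote Month 1 assessment from the mITT, so they are not imputed in the primary analysis.

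**The concern.** MCAR says that missingness is unrelated to any variable, site included. Under MCAR an observed-case analysis would already be unbiased and imputation would only recover precision. That fits poorly with adopting imputation because a pandemic raised the number of missing Month 1 ratings. It also does not match the method, since regression on treatment and earlier scores is justified by MAR given those variables.

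Site is the obvious candidate for something that drives missed visits during a pandemic, and it defines the strata of the primary test. With site left out, missing scores are filled from a relationship common to all sites. If site predicts both missingness and the Month 1 score, the pooled rates can shift. The imputed site tables and the Breslow-Day test would also see sites drawn towards each other, although they are there to show site differences.

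**Working it through.** **No figure in the plan to reproduce.** The visible text gives no expected missing fraction, and the response-rate assumptions are blacked out. The rise in enrolment implies an allowance of (413 − 350)/413 = 15.3%. That allowance covers loss from the mITT; it is not the fraction missing within it.

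**What the method needs.** Let R be missingness of the Month 1 score Y, T treatment, X earlier scores and S site.

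- MCAR: P(R | Y, T, X, S) = P(R).
- Planned regression: valid if Y and R are independent given T and X.
- Leaving out S breaks this only if S predicts R **and** S still predicts Y after T and X are known.

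Day 7 and Day 14 scores carry much of a site's treatment response, so the second link is weak when they are observed. It is stronger when they are missing too and X reduces to baseline.

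**Simulation A (all inputs assumed).** 118 vs 59 subjects, 15 sites, five imputations, Day 7/14 fully observed, 300 runs per scenario. Missingness is concentrated in the five sites with the weakest active effect: 25.5% there and 2.25% elsewhere, so (5 × 25.5 + 10 × 2.25)/15 = 10%; or 38.25% and 3.375%, giving 15%. The site version has site and site-by-treatment terms, which is more than the fix proposed here. Mantel-Haenszel risk differences:

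| Site SD (grade) | Missing | Full data | MI as planned | MI with site terms | Observed cases | BOCF |
|---|---|---|---|---|---|---|
| 0 | 10% | 0.756 | 0.748 | 0.743 | 0.757 | 0.682 |
| 0 | 15% | 0.751 | 0.739 | 0.730 | 0.751 | 0.638 |
| 0.3 | 10% | 0.740 | 0.735 | 0.728 | 0.755 | 0.678 |
| 0.3 | 15% | 0.740 | 0.732 | 0.718 | 0.759 | 0.645 |
| 0.6 | 10% | 0.701 | 0.697 | 0.691 | 0.727 | 0.652 |
| 0.6 | 15% | 0.700 | 0.694 | 0.682 | 0.740 | 0.624 |

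Planned MI is 0.4 to 1.2 points from full data. The site terms move it a further 0.5 to 1.4 points away. The 5th percentile of the smallest CMH chi-square across imputations is 53.9 or more, so significance is never in doubt.

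**Simulation B (assumed inputs).** 100 vs 50 subjects, 15 sites, 30% missing at four sites and 3% elsewhere, site SD 0.3 to 0.6 grade, Day 7/14 observed, 400 runs, site as a main effect only. Planned MI is 0.1 to 1.1 points below the full-data active rate. Adding site moves it a further 0.2 to 0.5 point away.

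**Simulation C (assumed inputs).** All four arms, 350 subjects, 15 sites, site as a main effect.

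- Day 7/14 observed: adding site shifts bias by under 0.5 point.
- Day 7/14 also missing, with hard-hit sites responding worst: bias usually falls from about 0.8–2.1 points to 0.0–0.9, a gain of about 0.5 to 1.3 points in most scenarios.

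**Cell sizes.** Per site on average: 350/15 = 23.3 subjects across all arms, 100/15 = 6.7 per active arm and 50/15 = 3.3 on placebo. A main effect fitted across arms can be estimated; site-by-treatment terms would be thin.

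**The case against.** The strongest objection is that the label changes no computation and that adding site does not help. Regression MI on treatment and earlier scores is valid under MAR whatever the SAP calls it, and simulations A and B show site terms moving the estimate slightly away from full data. Observed-case mITT analyses of both endpoints are also planned (Tables 14.2.1.3.4 and 14.2.2.3.4). With a site-stratified CMH test these remain valid tests when missingness depends on site alone. The extra terms mean up to 14 indicators in each of six regressions.

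Much of this stands. It does not remove the point, because the stated assumption of the primary analysis is still unsupported. Simulations A and B assume complete Day 7/14 data, the case in which site matters least. No planned sensitivity analysis puts site into the imputation.

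Three stronger readings are tempting, and the documents do not support them:

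- *The documents contradict MCAR, and imputed values will cluster by site.* The wording about local restrictions explains the remote assessments, and subjects assessed remotely at Month 1 leave the mITT. Clustering is an inference from the Protocol 12.1 rationale, the by-site summary of COVID-related deviations (SAP 2.3.2) and the planned listing of assessments missed because of COVID-19 (SAP 4.2).
- *The primary rate is biased by up to 2 points, or the stratified test is invalid.* Filling gaps with the arm mean does give 0 to 2.0 points under assumed inputs (30% missing at four of 15 sites, 3% elsewhere), but the plan uses each subject's own earlier scores. The rates, differences and Wald intervals in SAP 2.4.3 are described by treatment group without site weighting.
- *Site was left out because MCAR was assumed.* Nothing links the two.

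**Conclusion.** The point holds as a correction to the stated assumption and as inexpensive protection in the imputation model. MCAR is unsupported and stronger than the method needs; MAR is the assumption actually relied on. Leaving out site is out of line with the randomisation, the primary test and the imputed site tables, but the expected effect on the overall result is small. It is near zero when Day 7/14 scores are observed. About 0.5 to 1.3 points of bias could be avoided in most scenarios where those scores are also missing and missingness follows site response. No change in significance is expected. These sizes rest on assumed site variation, missing fractions and response patterns, none of which the documents give.

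**What to change.** In SAP 2.4.2, replace the MCAR statement with: missing at random given treatment group, earlier scores and site. Add the site strata of the CMH test as a main effect to each imputation regression, and say that the regressions are fitted across all four arms. If the pooling in SAP 2.1.2 is triggered, use those regions instead; they are already to be set before unblinding.

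The cost is one reworded sentence and up to 14 indicators per regression, with no new data. The downside is a bias shift of up to about 0.5 point where site is not needed. If the sponsor prefers to leave site out, the SAP should say so and justify it by the small site-by-arm cells.
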